hematologic response in ~40% subjects, with most responses occurring with the lenalidomide/dexamethasone combination. A variety of toxicities have been observed, including leukopenia, rash, venous thrombosis, and intolerance to the dexamethasone. This report indicated better tolerability than thalidomide, however, 20% of subjects still stopped treatment with lenalidomide due to toxicities. We have extended our study to subjects on dialysis, using attenuated doses, with good preliminary results. A study using lenalidomide in combination with melphalan and dexamethasone is ongoing; this study is not suitable for subjects with significant prior exposure to alkylator agent.

Pomalidomide (CC4047), a 2nd generation immune-modulatory drug, has shown promising activity in phase-2 trial in combination with low-dose dexamethasone for relapsed or refractory multiple myeloma and AL amyloidosis. Responses were seen in 50% of subjects previously-failing thalidomide and/or lenalidomide in AL amyloidosis.

Given these promising results of pomalidomide in plasma cell dyscrasias, we propose a study of pomalidomide and low dose dexamethasone in persons with previously-treated AL amyloidosis.

STUDY OBJECTIVES:

Primary:

• Determine dose-limiting toxicity (DLT) and the maximum tolerated dose (MTD) of pomalidomide combined with dexamethasone in persons with previously-treated light-chain (AL)-amyloidosis.

Secondary:

- Determine the following at the MTD:
 - Hematological complete (CR) very good partial (VGPR) and partial (PR) rates
 - Response-duration
 - Organ response
 - Time-to-event
 - Survival

Exploratory:

• To investigate the relationship of changes in the levels of the biomarkers BNP and troponin I to frequency of specific adverse events and the occurrence of DLT.

STUDY DESIGN:

Phase-I/II dose-escalation study of pomalidomide and dexamethasone in persons with previously-treated AL-amyloidosis. During the Phase I portion the MTD will be determined based on DLTs in the first cycle. At the MTD an expanded cohort of 12 subjects will be evaluated to estimate efficacy.

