5.1 Overall design

STUDY DESIGN:

Phase I/II dose-escalation study of pomalidomide and dexamethasone in persons with previously-treated AL-amyloidosis. During the Phase I portion the MTD will be determined based on DLT in the first cycle. At the MTD an expanded cohort of 12 subjects will be evaluated to estimate efficacy.

The study includes a screening period, a treatment (dose escalation) period, and a follow-up period for survival. After giving written informed consent, subjects will be evaluated for eligibility for enrollment in the study and baseline evaluations will be performed. Subjects who satisfy all inclusion and exclusion criteria will begin study drug treatment with dose escalation. Standard dose escalation rules will be used.

Subjects will be monitored every cycle for safety, hematological status, and organ function during therapy or until the occurrence of progressive disease (PD).

Treatment Group Assignments and Subject Replacement

This is a dose-escalation study and dose escalation will proceed through 3 dose-levels according to standard rules in which dose levels are started sequentially after complete evaluation of the occurrence of DLT. Based on the dose escalation scheme, as many as 30 subjects could be enrolled in the study. Subjects who discontinue pomalidomide for reasons other than DLT before completing at least 2 treatment cycles are to be replaced.

Subpopulations

An additional 12 subjects will be enrolled in an expanded cohort for analysis of efficacy at each schedule studied.

Subjects in this cohort will be treated at the dose defined as the MTD for that schedule.

Pomalidomide

Schema:

Phase I:

Pomalidomide 2 mg/day D1-21 – dose escalation to 4 mg/day by 1 mg units* Dexamethasone 10-20 mg D1, 8, 15, 22

* Pomalidomide dosing for Phase I cohorts 1 and 2 given on days 1-28 of a 28-day cycle and changed to Days 1-21 of a 28 day cycle with Cohort 3.

This cycle will be repeated every 28 days.

Subjects will take aspirin 325 mg/day to prevent venous thrombosis whilst on-study. A proton pump inhibitor will be used for GI prophylaxis.

Phase II:

Pomalidomide [MTD] mg/day D1-21 Dexamethasone 10-20 mg D1, 8, 15, 22

This cycle will be repeated every 28 days.

Subjects will take aspirin 325 mg/day for prophylaxis against venous thrombosis while on study. A proton pump inhibitor will be used for GI prophylaxis.

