5.4.2 Dosing regimen

The initial planned dose of pomalidomide for investigation is 2 mg/day, orally on days 1 - 21 (28 day cycle).* Dosing will be in the evening at approximately the same time each day,

either 2 hours before or 2 hours after food ingestion. Participants will be instructed to avoid smoking, as smoking can decrease the efficacy of pomalidomide. Only enough pomalidomide for one cycle of therapy will be supplied to the subject each cycle.

* Pomalidomide dosing for Phase I cohorts 1 and 2 given on days 1-28 of a 28-day cycle and changed to Days 1-21 of a 28 day cycle with Cohort 3.

The planned dose levels of Pomalidomide are presented below in Table 15-1 table.

		Enrollment (Number of Subjects)					
Dose Group	Pomalidomide Dose (mg/dose)	Initial	Expanded at MTD ^a				
1	2	3 ^b	3				
2	3	3	3	12			
3	4	3	3				

Table 15-1 Planned Study Drug Doses

a. Twelve additional subjects are to be enrolled in an expanded cohort for analysis of efficacy and treated at the MTD for each dosing schedule.

b. If the first 2 subjects enrolled experience DLT then this cohort is closed and further subjects will be evaluated at 1mg/day dose and the cohort expanded at that dose.

The dose escalation rules will follow the standard Fibonacci method.

Dose escalation algorithm

At least 3 subjects are to be enrolled in each dose group, beginning with the 2 mg/dose. Within each dose group, 3 subjects are to complete at least 2 treatment cycles. It is noted that if the first 2 subjects in the first cohort develop DLT, then the cohort at the 1 mg/dose dose will be defined as the MTD.

Dose escalation within a cohort is not allowed.

- If after all 3 subjects complete 1 treatment cycle:
 - No subject experiences DLT, then enrollment at the next planned dose level may commence.
 - One subject experiences DLT, then 3 additional subjects are to be enrolled at the current dose level.
 - If 1 of 6 subjects experiences DLT, then enrollment at the next planned dose level may commence.
 - If 2 or more of 6 subjects experience DLT, then the previous dose is declared the MTD.

Two or more subjects experience DLT, then the previous dose is declared the MTD.

- Dose escalation continues through the 3 dose levels in order to define the MTD based on the occurrence of DLT in the first cycle. Definitions of DLT and MTD are as follows:

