10.3 Statistical Methodology

Determination of Sample Size

Based on the dose escalation scheme, as many as 30 subjects may be enrolled in this study.

The number of subjects enrolled will depend on the outcome of the actual dose escalation process. The dose-escalation phase consists of 3 cohorts, each with 2 to 6 subjects enrolled depending on when DLT occurs. Therefore, a minimum of 2 and a maximum of 18 subjects will be enrolled in this phase.

An additional 12 subjects will be enrolled in an expanded cohort for efficacy at each schedule. Therefore, an additional 12 subjects could potentially be enrolled.

It is expected that approximately 30 patients will be enrolled in the phase I/II portions of this study. The endpoints measured in the protocol will be overall response rate (ORR) determined by either CR, VGPR or PR and response of one or more organs. It is estimated by the principle investigator's approximate frequency of response in 18 patients (6 patients will be dosed at the MTD during the phase I portion of this trial plus the additional 12 patients at this MTD dose during the phase II portion). Using the adjusted Wald's confidence interval for the proportion and the corresponding point estimates for hypothetical data, it is expected that if 6 out of 18 have ORR then the estimated response rate would be 35.57% with a 90% confidence interval between 18.21% and 52.81% with similar estimates for organ response.

Randomization and Stratification This is not a randomized study.

Populations for Analysis

The safety population will include all subjects who received at least 1 dose of study drug.

The additional 12 subjects enrolled in the expanded cohort for efficacy will comprise the efficacy population.

Procedures for Handling Missing, Unused, and Spurious Data

No imputation of values for missing data will be performed. Standard clinical monitoring and data management practices will be used to ensure the integrity of data.

General Methodology

In general, summary tabulations will be presented by dose group showing the number of observations, mean, standard deviation, median, minimum, and maximum for continuous variables, and the number and percent (calculated using non-missing values) per category for categorical data.

Safety Analysis

• Determination of MTD

The determination of MTD will be achieved by the results of a deterministic algorithm; thus, statistical hypothesis testing is not intended.

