The evaluation of MTD will be based on data from subjects who receive pomalidomide and whose data are interpretable in the context of study drug-specific toxicity (ie, subjects should have had sufficient safety assessments performed to determine whether DLT occurred and should not have received alternate antineoplastic therapies through cycle 1). Subjects who are withdrawn from the study for reasons other than DLT before completing cycle 1 and are replaced consequently will not be included in the analysis of MTD. Subjects will be analyzed according to the dose actually received.

Pharmacokinetics/Pharmacodynamics Not applicable.

Efficacy Analysis

The efficacy analysis will be based on confirmed hematological response and confirmed organ response. The analysis of response data at the MTD will be descriptive, consisting of 2-sided 90% confidence intervals.

Additional analyses of efficacy data at the MTD will consist of evaluations of time to hematologic response, duration of hematologic response, and time to worsening of hematologic and/or organ function. These analyses will also be descriptive in nature.

Analysis of the rates of responders for each of the other dose levels will also be presented, without calculation of confidence intervals.

Exploratory Analysis

An exploratory analysis will be conducted to investigate the relationship of changes in the levels of the biomarkers brain natriuretic peptide (BNP) and troponin I to the frequency of specific AEs and the occurrence of DLT. Additionally, the benefit, if any, of using these measures in addition to routine monitoring by ECG and echocardiogram will be explored. The frequency of conversion in immunofixation results from positive to negative will be explored and the disappearance of free light chain. Efficacy at additional doses may be explored for potential use in future Phase II clinical trials.

Interim Analysis

Interim analyses will be performed following each cohort during the Phase I portion of the study. No interim analysis is planned for the Phase II portion.

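### Response-rate precision is stated for 18 subjects at the MTD, but the efficacy population is defined as the 12 expansion subjects, who cannot deliver it

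*Combined protocol and SAP*

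**What the plan says.** Section 10.3, Determination of Sample Size, takes its denominator from two groups: "6 patients will be dosed at the MTD during the phase I portion of this trial plus the additional 12 patients at this MTD dose", making 18. For 6 responders it then states that "the estimated response rate would be 35.57% with a 90% confidence interval between 18.21% and 52.81" per cent, by the adjusted Wald method, and expects similar figures for organ response.

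Further down the same section, Populations for Analysis reads: "The additional 12 subjects enrolled in the expanded cohort for efficacy will comprise the efficacy population".

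Other places link efficacy to the 12. The synopsis and section 5.1 say: "At the MTD an expanded cohort of 12 subjects will be evaluated to estimate efficacy". Footnote a to Table 15-1 in section 5.4.2 says: "Twelve additional subjects are to be enrolled in an expanded cohort for analysis of efficacy and treated at the MTD for each dosing schedule". On dose, section 5.1 adds: "Subjects in this cohort will be treated at the dose defined as the MTD for that schedule".

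The Efficacy Analysis text in section 10.3 names no population. It says: "The analysis of response data at the MTD will be descriptive, consisting of 2-sided 90% confidence intervals". It also plans to report response outside the MTD: "Analysis of the rates of responders for each of the other dose levels will also be presented, without calculation of confidence intervals". Section 10.6, headed as sample size and power, has no text beneath its heading.

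**The concern.** The two denominators describe the same estimate. If the population definition governs, the 6 Phase I subjects are out and the printed interval is narrower than the analysis can produce. If the sample-size paragraph governs, the population definition is wrong.

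The expansion cohort exists to estimate efficacy, and this interval is the only statement of how well it will do so. There is also a question of discipline. With both 12 and 18 in writing, the choice could be made after it is known whether the Phase I subjects at the MTD responded. In a cohort this small, a few responders move the estimate visibly.

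**Working it through.** **Inputs (all from section 10.3).** Two-sided 90% confidence; adjusted Wald interval; 6 responders of 18 in the illustration; efficacy population of 12. The matching case at n = 12 is 4 responders, since 4/12 = 6/18 = 33.3%.

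**Formula.** With z = 1.64485 and z² = 2.7055:

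- centre = (x + z²/2) / (n + z²) = (x + 1.3528) / (n + 2.7055)
- half-width = z × √[centre × (1 − centre) / (n + 2.7055)]

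**Step 1: reproduce the plan's figure, 6/18.**

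- centre = 7.3528 / 20.7055 = 35.51%
- half-width = 1.64485 × √(0.35511 × 0.64489 / 20.7055) = 17.30 points
- interval = 18.21% to 52.81%

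Both printed limits are matched to two decimals. Other common methods do not match at 6/18: plain Wald gives 15.06% to 51.61%, Wilson 18.33% to 52.69%, Clopper-Pearson 15.63% to 55.40%, and the version adding 2 responders and 4 subjects gives 19.49% to 53.23%. The printed interval is therefore an n = 18 result by the stated method.

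The printed point estimate is not matched. The adjusted centre is 35.51%, which is also the midpoint of the printed limits: (18.21 + 52.81)/2 = 35.51. The plan prints 35.57%, a slip of 0.06 points.

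**Step 2: the same rate in the defined population, 4/12.**

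- centre = 5.3528 / 14.7055 = 36.40%
- half-width = 1.64485 × √(0.36400 × 0.63600 / 14.7055) = 20.64 points
- interval = 15.76% to 57.04%

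**Step 3: compare.** The half-width difference is 20.64 − 17.30 = 3.34 points, a ratio of 1.193. The full width goes from 34.60 to 41.28 points.

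**Step 4: does the example rate matter?**

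| Observed rate | Half-width, n = 18 | Half-width, n = 12 | Difference | Ratio |
|---|---|---|---|---|
| 1/6 (3/18, 2/12) | 14.73 | 18.00 | 3.27 | 1.22 |
| 1/3 (6/18, 4/12) | 17.30 | 20.64 | 3.34 | 1.19 |
| 1/2 (9/18, 6/12) | 18.07 | 21.45 | 3.37 | 1.19 |

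A rate of 2/3 mirrors 1/3. The loss is about 3.3 points, or 19% to 22%, throughout.

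**Step 5: can the Phase I subjects be assumed to belong?** Not from the text as it stands.

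- *Schedule of Phase I.* Cohorts 1 and 2 were dosed on days 1-28; the schedule changed to days 1-21 with Cohort 3 (sections 5.1, 5.4.1, 5.4.2).
- *Schedule of Phase II.* It is days 1-21 in the synopsis schema and sections 5.1 and 5.4.1, but days 1-28 in the synopsis dosing-regimen box. Table 1 of section 5.5.2, covering both phases, gives days 1-28 for the starting dose at the MTD.
- *Maximum planned dose.* Section 10.1 describes 4 mg/day as continuous; section 5.4.1 gives it on days 1-21.
- *Number.* Section 5.4.1 requires at least 6 subjects at the MTD before Phase II, so 6 is a minimum. It also lets Phase I subjects increase to the MTD later.
- *Replacement.* Section 5.1 replaces subjects who stop before two cycles for reasons other than DLT. The exclusion of replaced subjects in section 10.3 covers the MTD determination and is silent on response.

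**The case against.** The best case is that 18 was intended and the population sentence is the stray one. The derivation of 18 is explicit. The 90% intervals are attached to response data at the MTD, not to the efficacy population. The secondary objectives are set at the MTD, and the efficacy look in section 10.5.2 counts the first four subjects treated at the MTD. The passages that enrol 12 subjects for efficacy do not say that Phase I subjects are excluded. The interval is also offered as an illustration from hypothetical data, for a secondary endpoint with no test or threshold, and both intervals are wide.

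Much of this stands as a caution: the intended denominator is not certain, and the consequence is moderate. It does not remove the conflict. The only sentence that defines an efficacy population limits it to 12, and none of the passages favouring 18 overrides it. What is hypothetical in the illustration is the number of responders; the 18 is stated as a feature of the design.

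The schedule problem is conditional. If the MTD comes from Cohort 3 and Phase II runs on days 1-21, the schedules agree. It bites if the MTD comes from Cohort 1 or 2, or if the days 1-28 text applies to Phase II.

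**Conclusion.** The point holds. Under the plan's own definition of the efficacy population, the stated precision is not achieved: at an observed rate of one third the 90% interval is 15.8% to 57.0%, not 18.2% to 52.8%, and the half-width is 20.6 instead of 17.3 points. This rests on the adjusted Wald method at two-sided 90%, as the plan specifies, on equal observed rates, and on all 12 expansion subjects being evaluable.

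No power or error rate is affected and no decision depends on the interval. It should be corrected because it is the sole precision statement for response and because the denominator should be fixed before responses are analysed. The 35.57% figure is a minor separate error.

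**What to change.** Before response data are analysed, make the sample-size paragraph, the population definition and the Efficacy Analysis text in section 10.3 agree.

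- **Option A: pool.** Define the population for the MTD response rate as all subjects who started treatment at the MTD on the expansion schedule, Phase I and expansion together. State that n depends on how many Phase I subjects qualify, and show 6/18 (18.2% to 52.8%) and 4/12 (15.8% to 57.0%) as the n = 18 and n = 12 cases. Say whether a replaced subject and the replacement both count. List separately those who increased to the MTD later.
- **Option B: expansion only.** Keep the 12 and restate the precision as 4/12: 15.8% to 57.0%.

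Under either option, name the chosen population where the 90% intervals are specified, and correct 35.57% to 35.51% wherever the 6/18 example is kept. Because pooling depends on schedule, the conflicting statements in the synopsis and sections 5.1, 5.4.1, 5.5.2 and 10.1 must be reconciled and read with the wording that ties the MTD to its schedule.

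The cost is wording and one restated interval, with no extra patients. If n is 12, the sponsor must accept a half-width of 20.6 points.

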- DLT Based on the first cycle; toxicity considered by the investigator to be related to Pomalidomide; Grade 4 thrombocytopenia or neutropenia; ≥ Grade 3 nonhematologic toxicity
- MTD The dose level at which DLT occurs in no more than 1 of 6 subjects (ie, the dose level below that at which DLT was established).

Subjects will take aspirin 325 mg/day to prevent venous thrombosis while on pomalidomide.

A proton pump inhibitor will be used for GI prophylaxis.

Pomalidomide capsules should be swallowed whole, and should not be broken, chewed or opened. Pomalidomide should be taken without food, at least 2 hours before or 2 hours after a meal.

If a dose of pomalidomide is missed, it should be taken as soon as possible on the same day. If it is missed for the entire day, it should not be made up, rather it should be taken as usual at the next scheduled time.

Subjects who take more than the prescribed dose of pomalidomide should be instructed to seek emergency medical care if needed and contact study staff immediately.

Subjects experiencing adverse events may need study treatment modifications (See section 5.5).

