other non-hematologic toxicity ≥ Grade 3	 Hold (interrupt) pomalidomide dose. Follow at least weekly. If the toxicity resolves to ≤ grade 2 prior to Day 21, restart pomalidomide at next lower dose level and continue the cycle. 	 Omit pomalidomide for remainder of cycle. See Instructions for Initiation of a New Cycle and reduce the dose of pomalidomide by 1 dose level. 	
Hyperthyroidism or hypothyroidism ≥ Grade 2	 Omit pomalidomide for remainder of cycle, evaluate etiology, and initiate appropriate therapy. If the toxicity resolves to ≤ grade 1 prior to Day 21, restart pomalidomide at next lower dose level and continue the cycle. 	 Omit pomalidomide for remainder of cycle, evaluate etiology, and initiate appropriate therapy. See Instructions for Initiation of a New Cycle and reduce the dose of pomalidomide by 1 dose level. 	
Any attributable or non- attributable hospitalization or toxicity grade < 2	 Pomalidomide may be held or continued at the discretion of the treating investigator. Once resumed, maintain dose level. 	 Pomalidomide may be held or continued at the discretion of the treating investigator. If held, see Instructions for Initiation of a New Cycle and maintain dose level. 	

¥ As stated in the table, pomalidomide should be held for occurrence of grade 3 neutropenia with fever or grade 4 neutropenia attributable to Pomalidomide. Follow CBC weekly.

If neutropenia has resolved to \leq grade 2 prior to Day 21, restart pomalidomide at next lower dose level and continue the cycle. If neutropenia is the only toxicity for which a dose reduction is required, G-CSF may be used and the pomalidomide dose can be maintained. In case of second occurrences of Grade 4 neutropenia or Grade 3 neutropenia with fever in the setting of GCSF, pomalidomide will be held and if neutropenia has resolved to \leq grade 2 prior to Day 21, restart pomalidomide at next lower dose level with addition of G-CSF

Table 4: Non-hematological toxicity attributable to dexamethasone			
	Grade 1-2	Grade 3-4	
Dyspepsia / Gl	Start H2-blocker or Proton Pump Inhibitor if not already on one of these.	Hold dexamethasone and start H2- blocker or Proton Pump Inhibitor if not already on one of these. Once toxicity has decreased to Grade 0-2, resume Dex at one dosing level lower with continued H2B or PPI. If Grade 3-4 toxicity persists for more than 14	

Dose Modifications for Dexamethasone

		days,endoscopy or other UGI
		evaluation is encouraged.

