5.5.3 Treatment compliance

At all times, when dispensing study drug, research center personnel will review the instructions, printed on the packaging, with subjects. Subjects will be asked to maintain a diary to record the drug administration. Subjects will be asked to bring any unused study drug and empty study drug containers to the research center at their next visit. Research personnel will count and record the number of used and unused study drug capsules at each visit and reconcile with the subject diary.

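### Section 10.3 sets no minimum Cycle 1 exposure for the MTD count, so an under-dosed subject who stays on study can be counted as DLT-free

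*Combined protocol and SAP*

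**What the plan says.** **Who counts.** Section 10.3 (Determination of MTD) bases the MTD on subjects who receive pomalidomide and whose data can be interpreted for drug-specific toxicity. It spells this out as: "subjects should have had sufficient safety assessments performed to determine whether DLT occurred and should not have received alternate antineoplastic therapies through cycle 1".

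**Who does not count.** The next sentence sets an exclusion from the MTD analysis: "Subjects who are withdrawn from the study for reasons other than DLT before completing cycle 1 and are replaced consequently will not be included in" that analysis. Section 5.1 adds: "Subjects who discontinue pomalidomide for reasons other than DLT before completing at least 2 treatment cycles are to be replaced". Section 5.4.2 adds: "Within each dose group, 3 subjects are to complete at least 2 treatment cycles". The escalation decision itself is taken once three subjects have completed one cycle.

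**Dose attribution.** Section 10.3 says: "Subjects will be analyzed according to the dose actually received". It does not say whether this means the assigned level, the cumulative dose or the dose intensity.

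**Missed and held doses.** On a missed dose, Section 5.4.2 says "If it is missed for the entire day, it should" not be made up, and it sets no limit on how many may be missed. Section 5.5.1 bars dose modification in Cycle 1 unless a DLT has been documented. Table 3 (Section 5.5.4) nevertheless interrupts or omits pomalidomide for events below the DLT threshold, with no exception for Cycle 1. Examples are Grade 3 thrombocytopenia (the hematologic DLT threshold is Grade 4) and Grade 2 thyroid toxicity. Its last row, on hospitalization and low-grade toxicity, says: "Pomalidomide may be held or continued at the discretion of the treating investigator".

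**Exposure data.** Under Treatment compliance, staff "count and record the number of used and unused study drug capsules at each visit" and reconcile the count with the subject's diary.

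**The concern.** A DLT-free Cycle 1 is evidence about a dose only if the subject took most of that dose. The rule in Section 10.3 tests whether the subject was observed and whether other therapy was given. It does not test whether the study drug was taken. The exclusion and replacement rules apply to leaving treatment, so they do not reach a subject who remains on study with little drug.

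The toxicity-driven holds matter most. Stopping drug at Grade 3 thrombocytopenia may prevent the Grade 4 event that would have been a DLT, yet under the stated rule the subject can enter the count as DLT-free.

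The MTD is the primary endpoint (Section 4.2.1) and rests on three to six subjects per level. An overstated MTD would carry into the 12-subject expansion. It would also affect Phase I subjects who may be offered an increase to the MTD (Section 5.4.1).

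**Working it through.** **1. The plan's own figures.** Three levels of at most six subjects give 3 × 6 = 18, and 18 + 12 = 30. Both match Section 10.3. The plan states no operating characteristics for the MTD rule, so there is no further figure to reproduce.

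**2. Does any rule require exposure?**

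| Rule | What triggers it | Reaches a subject on study with few doses and no DLT? |
|---|---|---|
| 10.3, interpretable data | Too few safety assessments, or other antineoplastic therapy | No |
| 10.3, exclusion | Non-DLT withdrawal before completing Cycle 1, with replacement | No |
| 5.1, replacement | Non-DLT discontinuation before two cycles | No |
| 5.4.2, cycle completion | Not completing cycles | Unclear: completion is not defined by doses taken |
| 10.3, dose received | Partial dosing, possibly | Unclear: not defined |
| 5.5.1, Cycle 1 rule | Dose modification without a DLT | Silent on missed doses; conflicts with Table 3 on holds |

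**3. How low can intake go under Table 3?** A hold starting on Day 15 leaves 14 doses taken. That is 14/21 = 67% on the Day 1–21 schedule, or 14/28 = 50% on the Day 1–28 schedule of cohorts 1 and 2. An earlier hold that is not lifted leaves less.

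**4. Effect on clearing one dose level.** Under Section 5.4.2 a level is cleared with 0/3 DLTs, or with 1/3 followed by 0/3. Let p be the full-dose DLT risk and q the risk of one under-exposed subject among the first three.

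- All fully exposed: (1−p)³ + 3p(1−p)² × (1−p)³
- One under-exposed: (1−q)(1−p)² + [(1−q) × 2p(1−p) + q(1−p)²] × (1−p)³

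For p = 0.40:

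- All fully exposed: 0.216 + 0.432 × 0.216 = 0.309
- q = 0.10: 0.324 + 0.468 × 0.216 = 0.425
- q = 0: 0.360 + 0.480 × 0.216 = 0.464
- q = 0.20 (half of p): 0.288 + 0.456 × 0.216 = 0.386

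| True p | All fully exposed | q = half of p | q = 0.10 | q = 0 |
|---|---|---|---|---|
| 0.33 | 0.434 | 0.508 | 0.537 | 0.582 |
| 0.40 | 0.309 | 0.386 | 0.425 | 0.464 |
| 0.50 | 0.172 | 0.242 | 0.284 | 0.312 |

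**5. Effect on the MTD criterion.** The MTD definition allows at most 1 DLT in 6.

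- All fully exposed: (1−p)⁶ + 6p(1−p)⁵
- One under-exposed: (1−q)[(1−p)⁵ + 5p(1−p)⁴] + q(1−p)⁵

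For p = 0.40:

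- All fully exposed: 0.0467 + 0.1866 = 0.233
- q = 0.10: 0.9 × 0.3370 + 0.1 × 0.0778 = 0.311
- q = 0: 0.0778 + 0.2592 = 0.337
- q = 0.20: 0.8 × 0.3370 + 0.2 × 0.0778 = 0.285

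For q from 0.10 down to 0, p = 0.33 goes from 36% to 43–47%, and p = 0.50 from 11% to 17–19%.

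**6. Without assuming that such a subject is present.** Suppose a fraction f of counted subjects has no DLT risk, so the counted risk is p(1−f). Assume true risks of 15%, 30% and 50% at 2, 3 and 4 mg. The chance that all three levels are cleared is the product of the step 4 probabilities:

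- f = 0: 0.814 × 0.494 × 0.172 = 0.069
- f = 10%: 0.843 × 0.557 × 0.234 = 0.110
- f = 20%: 0.871 × 0.622 × 0.309 = 0.168

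The values of p, q and f are assumptions; none is given in the documents.

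**The case against.** The strongest reply is that the plan already narrows the gap. A subject who takes few doses and then leaves for a non-DLT reason is excluded and replaced. A related cardiac or renal event of Grade 3 or higher is itself a DLT. Section 5.5.1 can be read as barring Cycle 1 holds without a DLT, since Table 3 is titled as dose modifications and lists holds among them. The sentence on analysis by dose received is at least in tension with crediting a partly dosed subject to the full dose. The remaining case is a subject who is off drug for much of Cycle 1, has no DLT, has not discontinued, and is still judged interpretable.

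Most of this stands as a limit on the point, but it does not remove it. Missed doses fall outside Section 5.5.1. The heading of Section 5.5.4 treats interruptions separately from modifications, so the bar may not reach holds at all. An undefined sentence on dose received cannot be relied on to remove the subject from the count.

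Three stronger readings are tempting, and the documents do not support them:

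- A reader might infer that every subject with few doses counts as tolerating the full dose. The withdrawal and replacement rules contradict this for those who leave, and no sentence says it of those who stay. It is a possibility left open by missing definitions.
- A reader might infer that under-exposure will be common because people with AL amyloidosis are often hospitalized. The documents give no hospitalization rate. Eligibility also excludes symptomatic arrhythmia, oxygen-dependent cardiomyopathy and dialysis. Whether the grade limit in the last row of Table 3 also applies to hospitalization is unclear.
- A reader might take the rise of 10 to 15 points in clearing one level as the expected error in the MTD. It assumes that an under-exposed subject is present and has close to no DLT risk. The six-subject criterion gives about 6 to 11 points on the same assumption, and 4 to 6 at half risk.

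**Conclusion.** The point holds in a limited form. The evaluability rule has no exposure requirement. Because neither cycle completion nor dose received is defined by doses taken, an under-dosed subject who stays on study can be counted as DLT-free. Section 5.5.1 and Table 3 conflict on Cycle 1 holds.

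If lower exposure lowers DLT risk, the bias is toward escalation. The summary case is a true DLT rate of 40% with one such subject at 0 to 10% risk: 31% becomes 43–46% for clearing a level, and 23% becomes 31–34% for the six-subject criterion. At half the full-dose risk the figures are 39% and 29%. The direction follows from the rule and that premise. The size cannot be fixed from the documents, because neither the frequency of under-exposure nor its DLT risk is given. The point is worth correcting because it bears on the primary endpoint and the exposure data are already collected.

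**What to change.** In Section 10.3:

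- Count a subject as MTD-evaluable only if a DLT occurred or a pre-stated share of planned Cycle 1 pomalidomide doses was taken, as judged from the capsule count and diary. State the share per schedule. At 80%, for example, 0.8 × 28 = 22.4 gives 23 of 28 days and 0.8 × 21 = 16.8 gives 17 of 21 days. The 80% is illustrative and has no source in the documents.
- Replace other subjects for the MTD count only, and keep them in the safety population.
- State separately how the MTD count treats subjects who are under-dosed because of drug-related toxicity below the DLT threshold. Replacing them without comment would discard toxicity evidence.
- Define, in doses taken, what completing Cycle 1 means, and define the dose received for a partly dosed subject.

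Section 5.5.1 and Table 3 must be reconciled on Cycle 1 holds without a DLT. Which provision governs is for the sponsor and investigators to decide.

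The cost is a short text change and possibly one or two replaced Phase I subjects. No new data collection is needed.
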